- r. Following the subject's written consent to participate in the study, all SAEs whether related or not related to study drug, must be collected, including those thought to be associated with protocol-specified procedures. Subjects with HBI-8000-related AEs of Grade ≥2 observed at the EoT visit should be followed-up and assessed monthly until the AEs have resolved to Grade ≤1 or are determined to be chronic or subject receives other anti-cancer therapy.
- s. Subject survival data will be collected by telephone contact or e-mail every 12 (±1) weeks after End-of-Treatment visit for up to 12 months after the last dose of HBI-8000 or until death.
- t. After discontinuation of HBI-8000 treatment, subjects without disease progression will be followed for progression with imaging of measurable disease every 12 (±1) weeks until progression, initiation of another anti-cancer treatment, or referral.

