### 2.2 Secondary Objectives

The secondary objectives of the study are:

- To evaluate the safety and tolerability of HBI-8000 in combination with a standard dose and regimen of pembrolizumab
- To explore the additional efficacy parameters for HBI-8000 in combination with a standard dose and regimen of pembrolizumab as measured by Disease Control Rate (DCR), Duration of Response (DoR), and Progression-Free Survival (PFS)

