### **3.1.2      Tumor Status and Survival Follow-Up**

Subjects without disease progression who completed up to 24 months of treatment or discontinued from HBI-8000 due to reasons other than PD are followed with imaging studies every 12 ( $\pm 1$ ) weeks until progression is documented, another anti-cancer treatment is initiated, or referral to hospice, whichever occurs first.

All subjects will be contacted approximately every 12 ( $\pm 1$ ) weeks by telephone contact or e-mail for survival follow-up for up to 12 months after the last dose of HBI-8000.

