#### **6.2.1.1.2 Survival Follow-up**

Post-treatment tumor status in subjects whose disease has not progressed, and survival follow-up will be conducted until study completion. Subjects for whom disease progression has not been observed will have assessments of tumor status every 12 weeks ( $\pm 1$  week) until a date of disease progression is obtained, initiation of another anti-cancer treatment, or referral to hospice. Survival will be followed approximately every 12 ( $\pm 1$ ) weeks by telephone contact or e-mail for up to 12 months after the last dose of HBI-8000.

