## 7 STATISTICAL CONSIDERATIONS

Statistical analyses will be performed using SAS® v9.4 or higher (SAS Institute, Cary NC, US). Continuous variables will be summarized using descriptive statistics (n, mean, standard deviation, median, minimum, and maximum). Categorical variables will be summarized showing the number and percentage (n, %) of subjects at each category. Time to event variables (i.e., PFS, DoR) will be analyzed using the Kaplan-Meier method. Where confidence limits are appropriate, the confidence level will be 95% (two-sided), unless otherwise stated. Individual data (including relevant derived variables) will be presented by parameter in listings. Results of statistical analyses, descriptive summary statistics and supportive listings will also be presented.

Detailed methodology for summary and statistical analyses of the data collected in this study will be documented in a Statistical Analysis Plan (SAP), which will be finalized and approved before database lock and maintained by the Sponsor. The SAP may modify the plans outlined in the protocol; however, any major modifications will also be reflected in a protocol amendment.

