### 7.5 Statistical Analyses

#### 7.5.1 Efficacy Analyses

Efficacy analyses will be performed on FAS and PPS. ORR will be estimated based on the proportion of subjects whose best overall response is CR or PR. Disease response will be assessed using RECIST v1.1 as the primary methodology and iRECIST will be used to exclude pseudo-progression when suspected. The estimate of the ORR will be accompanied by a 2-sided

95% exact binomial confidence interval (CI). DCR (CR+PR+SD) will be analyzed similarly. DOR and PFS will be summarized descriptively using Kaplan-Meier methods. The final SAP will provide more details on these analyses.

The efficacy endpoints are the following:

- **Objective Response Rate (ORR)**, defined as the percent of subjects with CR or PR according to RECIST 1.1 and irRECIST criteria, relative to the efficacy population. Subjects who do not have an on-study assessment due to safety issues will be included as non-responders.
- **Disease Control Rate (DCR)**, defined as the percent of subjects with CR, PR or SD according to RECIST 1.1 and iRECIST criteria, relative to the efficacy population.
- **Duration of Response (DoR)**, defined as the time from documentation of tumor response to disease progression.
- **Progression-Free Survival (PFS)**, defined as the time from the start of treatment (Day 1 Cycle 1) until objective tumor progression or death.

The EoT Safety Follow-up visit is scheduled  $30 \pm 3$  days after the last dosing of the HBI-8000 or before the initiation of new cancer treatment, whichever is earlier.

Response rate endpoints (ORR, DCR) will be summarized by number and percentage of subjects meeting the definition of ORR and DCR along with the corresponding exact 95% CI based on binomial distribution.

Time-to-event endpoints (DoR, and PFS) will be summarized by Kaplan-Meier methods (median, 95% CI, number of events, number censored, and Kaplan-Meier figures).

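### Duration of response ends at progression only, whereas PFS ends at progression or death, so a responder's death without documented progression would not count and durability would tend to be overstated

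*Combined protocol and SAP*

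**What the plan says.** Section 7.5.1 (Efficacy Analyses) lists four efficacy endpoints. DoR is "defined as the time from documentation of tumor response to disease progression". The PFS bullet directly below it starts at Cycle 1 Day 1 and runs "until objective tumor progression or death".

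Section 7 sends both to the same method: "Time to event variables (i.e., PFS, DoR) will be analyzed using the Kaplan-Meier method". Section 7.5.1 adds that the report will show medians, 95% confidence intervals, and the numbers of events and of censored subjects. It leaves further detail to a final SAP. Section 7 says that the SAP may modify the protocol's plans, with major changes also made by protocol amendment. No DoR rules from such a SAP are in the file.

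The synopsis, section 2.2 and section 2.3.2 name DoR but give it no end event. Section 2.2 makes it a secondary efficacy parameter.

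Two follow-up rules bear on the point. After HBI-8000 stops, subjects without progression are imaged every 12 (±1) weeks "until progression is documented, another anti-cancer treatment is initiated, or referral to hospice, whichever occurs first" (section 3.1.2; section 6.2.1.1.2 agrees). Survival contact by telephone or e-mail continues for up to 12 months after the last dose (Table 1, footnote s).

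**The concern.** A response can end in progression or in death. The PFS bullet covers both, and the DoR bullet covers only the first. A Kaplan-Meier analysis needs every responder classed as an event or as censored. A responder who dies without documented progression does not meet the stated DoR event, which leaves censoring. Censoring treats that responder as someone whose response could have gone on after death.

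The follow-up schedule leaves room for such deaths. Scans off treatment are 12 weeks apart and stop at hospice referral, while deaths are still collected.

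At stake is how durable the responses look in a single-arm study that section 7.1 says is meant to help plan later ones. DoR and PFS would also rest on different event rules in the same report. No hypothesis test or decision rule uses DoR. ORR, the sample size and the PFS event definition are not touched.

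**Working it through.** **The plan's own figures.** The documents state no DoR estimate. The only design figures are the adverse-event detection probabilities in Table 4. For a 10% event, 1−0.9^20 = 87.84% and 1−0.9^24 = 92.02%, against 87.8% and 92.0% stated. They reproduce but do not enter this point.

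**Inputs.** The event rules come from section 7.5.1. Let f be the share of response-ending events that are deaths without documented progression. The documents do not give f, so a range of 0 to 30% is assumed.

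**Direction.** This depends on the date at which a death is censored, which the documents do not state.

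- *Censored on the date of death.* The responder leaves the risk set at the same moment under either rule, but the progression-only rule omits a downward step. Its curve is therefore equal or higher at every time.
- *Censored at the last scan.* The responder leaves the risk set early, and the curve can be lower. Suppose responder A dies at month 10 with a last scan at month 8.5, and responder B progresses at month 9. Counting the death, S(9) = 1/2. With A censored at 8.5, only B is at risk at month 9, so S(9) = 0.

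The two conventions were compared by simulation with 8 responders, a 12-month true median and scans 0 to 12 weeks before death (all assumed). With censoring at the last scan, the progression-only curve dipped below the other somewhere in about 7% to 20% of trials for f of 5% to 30%. On average it was still higher. At f = 20% the 12-month estimate averaged about 0.57 under either convention, against 0.50 with deaths counted. The analytic value is 0.5^0.8 = 0.574.

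**Size.** Under constant, independent hazards, with deaths counted the median is ln2/(h_PD + h_death). With deaths censored it is ln2/h_PD. Since h_PD = (1−f)(h_PD + h_death), the ratio is 1/(1−f).

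| f (assumed) | 1/(1−f) | Inflation of median | An assumed 12-month median would read |
|---|---|---|---|
| 0% | 1.000 | 0% | 12.0 |
| 5% | 1.053 | 5% | 12.6 |
| 10% | 1.111 | 11% | 13.3 |
| 20% | 1.250 | 25% | 15.0 |
| 30% | 1.429 | 43% | 17.1 |

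**Small-sample check.** All inputs are assumed: 8 responders, 12-month true median, deaths censored at death, and follow-up to 34.6 months (24 + 12 months less 6 weeks). Section 3.1.1 lets treatment run past 24 months by agreement, so 34.6 is not a strict ceiling. When the curve equals exactly 0.5, the median is taken as the midpoint.

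| f | Typical median, deaths counted | Typical median, progression only | Trials with identical median |
|---|---|---|---|
| 5% | 12.2 | 12.7 | 77% |
| 10% | 12.1 | 13.2 | 59% |
| 20% | 12.3 | 15.0 | 34% |
| 30% | 12.2 | 16.9 | 17% |

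The 10th to 90th percentile range of the median with deaths counted is about 6.3 to 21.0 months, so the shift sits inside wide sampling noise.

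**The case against.** The strongest reply is that section 7.5.1 is a one-line definition with the detail expressly left to a SAP. Nowhere do the documents say that a responder's death is censored, and the SAP could still add death as an event. It is true that censoring is an inference and that the rule can still be corrected. But the protocol is not silent. It states an end event for DoR that omits death, beside one for PFS that includes it. A SAP that follows the protocol repeats the omission, and one that adds death departs from the stated definition until the two are aligned.

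A second reply is that the effect may be nil and is small next to the noise. That stands, and it limits the severity. It does not remove the point, because the error runs upward on average.

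A reader might go further than the documents allow in three ways.

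- One might infer that the reported curve can never be too low. That holds only with censoring on the date of death, as the two-responder example shows.
- One might read the percentages as a forecast for this trial. They are not, because f, the number of responders and the median are all assumed.
- Since imaging stops at new anti-cancer treatment, one might call the lack of a censoring rule for it part of the same error. It is a separate choice, for PFS as well as DoR, with its own trade-offs, and section 7.5.1 leaves such detail to the SAP.

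**Conclusion.** The point holds. The DoR definition in section 7.5.1 omits death, nothing else in the documents supplies it, and following the definition tends to overstate durability. The median is inflated by 1/(1−f)−1 under constant, independent hazards: 5% to 43% for assumed f of 5% to 30%, and nothing if no responder dies without documented progression. With about 8 responders the observed median would often not move when f is small.

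It should be corrected, but the consequence is modest because DoR is a descriptive secondary endpoint.

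**What to change.** In section 7.5.1 and in the SAP, define DoR among subjects with CR or PR as the time from documentation of the response to progression or death from any cause, whichever is first. State that the progression criteria and event rule are those used for PFS. This leaves the roles of RECIST 1.1 and irRECIST, and response confirmation, where the plan now has them. Any censoring rule for new anti-cancer treatment should be decided separately in the SAP.

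The cost is a wording change, best made before database lock. Deaths are already collected for up to 12 months after the last dose (section 3.1.2; Table 1, footnote s), so no new data are needed. The downside is that the reported median DoR may be shorter. Relative to the progression-only figure it falls by a fraction f under constant hazards, that is by 0% to 30% over the assumed range.

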## 7.5.2 Safety Analyses

The assessment of safety will include general safety information such as adverse events, vital signs, laboratory tests (hematology, biochemistry, coagulation, urinalysis), concomitant medications, and 12-lead ECGs.

All safety analyses will be conducted using the Safety Population. Descriptive statistics will be used to summarize safety data.

### 7.5.2.1 Adverse Events

Adverse events will be coded using the MedDRA classification system version 24.0 or higher. The severity of the events will be graded by the Investigator according to the NCI CTCAE version 5.0 or higher.

All adverse events (AEs) will be summarized, and emphasis will be placed on treatment-emergent adverse events (TEAEs). An AE will be considered treatment-emergent if it occurs or worsens in severity from pre-treatment state on or after the first dose date of any study treatment through 30 days after the last dose of any study treatment. All AEs will be listed.

An overall summary of AE will be provided by the frequency and percentage of subjects experiencing an AEs by MedDRA systems organ class (SOC) and preferred term (PT). TEAEs will be summarized by the frequency and percentage of subjects experiencing TEAEs SOC and

PT, and by worst NCI CTCAE severity grade. Summaries will also be provided for treatment related TEAEs, namely, those judged by the Investigator to be at least possibly related to study drug treatment.

Adverse events resulting in discontinuation from treatment or withdrawal from the study, Grade 3 or higher, serious adverse events, and deaths on-study will be tabulated.

All AEs noted during the study will be listed per subject, detailing reported term, system organ class, preferred term, start date, stop date, severity, relationship to each Treatment, TEAE flag, and outcome.

#### **7.5.2.2 Laboratory Tests**

Laboratory data will be summarized for the observed values at each scheduled assessment, together with the corresponding changes from baseline (the value obtained prior to dosing on Day 1 of Cycle 1) using descriptive statistics.

For those analytes that are gradable with CTCAE version 5.0 severity criteria, will be summarized by shift tables showing shifts from Baseline grade (i.e., grade prior to dosing on Day 1 of Cycle 1) and maximum severity grade on treatment.

Laboratory values outside the normal range will be flagged in the data listings.

#### **7.5.2.3 Vital Signs and Physical Examination**

Vital signs data will be summarized by the observed values at each scheduled assessment, together with the corresponding changes from baseline using descriptive statistics.

Physical examination findings will be presented in data listings.

#### **7.5.2.4 Concomitant Medications**

All documented and reported concomitant medications will be coded using the World Health Organization Drug Dictionary Enhanced (WHO DDE) version March 2021 or higher and classified by the Anatomical Therapeutic Chemical (ATC) classification system and preferred drug name (often the generic drug name).

#### **7.5.3 Interim Analyses**

No interim analyses are planned for this study.

#### **7.5.4 Guidance to Address a Pandemic or Other Global Health Emergencies and Potential Impact on the Clinical Study**

In the occurrence of a global health emergency affecting the conduct of the ongoing study, such as the coronavirus disease 2019 (COVID-19) pandemic, study conduct may be adjusted due to subjects being in self-isolation/quarantine, limited access to public places (including hospitals) due to the risk of spreading infections, and health care professionals being committed to critical tasks.

Adjustments to this protocol may be made as described below, in line with global regulatory authorities guidance in order to ensure the safety of study subjects, maintain compliance with GCP, and minimize the risks to study integrity during the COVID-19 pandemic [[FDA September 2020](#)]. Other countries may issue their own guidance requiring country specific recommendations to be followed.

### **Informed Consent**

If written consent by the study subject is not possible (for example because of physical isolation due to COVID-19 or other global health emergencies), consent could be given orally by the study subject and documented according to current regulatory guidance and IRB requirements.

Study subjects or the subject's legally authorized representative (LAR) and the Investigator/designee (person obtaining consent) could sign and date separate ICFs.

In case a written informed consent cannot be obtained at the clinical site, electronic informed consent can be obtained remotely. Alternatively, the consent form may be sent to the subject/LAR by facsimile, or e-mail, and the consent interview may then be conducted by telephone/telemedicine when the subject or subject's legally authorized representative can read the consent form during the discussion. If facsimile or email is not possible, the subject or subject's legally authorized representative will be requested to sign and date a blank piece of paper with a written statement affirming that subject agrees to participate in the study and documented according to the current regulatory guidance and IRB approval.

If re-consent is necessary for the implementation of **new urgent changes in study conduct** (mainly expected for reasons related to global health emergencies or important safety issues for other studies), alternative ways of obtaining consent may include contacting the study subject via phone or video-calls and obtaining oral consents, to be documented in the study subjects' medical records, supplemented with e-mail confirmation.

The informed consent procedure is to remain compliant with the study protocol as well as local regulatory requirements. All relevant records should be archived in the Investigator's site master file. A correctly signed and dated ICF should be obtained from the study subjects later, as soon as possible.

### **Study Visits and Procedures**

COVID-19 screening procedures that may be mandated by the health care system in which a clinical study is being conducted do not need to be reported as an amendment to the protocol even if done during clinical study visits. The Investigator in consultation with the Sponsor will decide if it is in the best interest of COVID-positive subjects to remain in the study.

In the case of missed visits due to global health emergencies (or other health pandemic) related reasons:

The site should make every effort to contact the study subject to confirm and document the reason for the missed visit, and at a minimum evaluate AEs/SAEs, and concomitant medications in order to assess subject safety.

## **8 SUPPORTING DOCUMENTATION AND OPERATIONAL CONSIDERATIONS**

### **8.1 Data Collection and Management**

#### **8.1.1 Electronic Case Report Forms**

Electronic Data Capture (EDC) will be used for this study, meaning that all eCRF data will be entered in electronic forms at the study center. Data collection will be completed by authorized study center staff designated by the Investigator. Appropriate training and security measures will be completed with the Investigator and all authorized study center staff prior to the study being initiated and any data being entered into the system for any study subjects.

All data must be entered in English. The eCRFs should always reflect the latest observations on the subjects participating in the study. Therefore, the eCRFs are to be completed as soon as possible during or after the subject's visit. To avoid inter-observer variability, every effort should be made to ensure that the same individual who made the initial baseline determinations completes all efficacy and safety evaluations. The Investigator must verify that all data entries in the eCRFs are accurate and correct. If some assessments are not done, or if certain information is not available or not applicable or unknown, the Investigator should indicate this in the eCRF. The Investigator will be required to electronically sign off on the clinical data.

#### **8.1.2 Source Documentation**

The eCRF is essentially considered a data entry form and should not constitute the original (or source) medical records unless otherwise specified. Source documents are all documents used by the Investigator or hospital that relate to the subject's medical history, that verify the existence of the subject, the inclusion and exclusion criteria and all records covering the subject's participation in the study. They include laboratory notes, electrocardiogram (ECG) results, memoranda, pharmacy dispensing records, subject files, etc.

The Investigator is responsible for maintaining source documents containing data that is attributable, legible, contemporaneous, original, accurate, complete, consistent, enduring, and available. Changes to source data should be traceable, should not obscure the original entry, and should be explained if necessary (e.g., via an audit trail). Source documents are to be made available for inspection by the study monitor at each monitoring visit. The Investigator must submit a completed eCRF for each subject who is enrolled, regardless of duration. All supportive documentation submitted with the eCRF, such as laboratory or hospital records, should be clearly identified with the study and subject number. Any personal information, including subject name, should be removed or redacted (deidentified) to preserve individual confidentiality.

#### **8.1.3 Data Management/Coding**

Data generated within this clinical study will be handled according to the relevant SOPs of the Data Management and Biostatistics departments of the Sponsor and CRO, where applicable.

Adverse events and medical history will be coded using the most current version of MedDRA. Concomitant medications will be coded using WHO Drug Dictionary Enhanced (WHO DDE).

## **8.2 Quality Control and Quality Assurance**

According to the Guidelines of Good Clinical Practice (GCP) (CPMP/ICH/135/95), the Sponsor is responsible for implementing and maintaining quality assurance and quality control systems with written SOPs.

Quality control will be applied to each stage of data handling.

The following steps will be taken to ensure the accuracy, consistency, completeness, reliability, and integrity of the data:

- Investigator meeting(s)
- Site initiation visit
- Early center visits post-enrollment
- Routine center monitoring
- Ongoing center communication and training
- Data management quality control checks
- Continuous data acquisition and cleaning
- Internal review of data
- Quality control check of the final clinical study report
- Investigator verification by electronically signing the eCRF
- In addition, the Sponsor or Sponsor representative(s) may conduct periodic audits of the study processes, including, but not limited to study center, vendors, clinical database, and final clinical study report.

